12.2.4 Analysis Endpoints

Efficacy and safety endpoints that will be evaluated for within- and/or between-treatment differences are listed below, followed by the descriptions of the derivations of selected endpoints

12.2.4.1 Efficacy Endpoints

Efficacy will be measured by percent PFS6 as defined by RANO.

12.2.4.2 Safety Endpoints

The primary safety endpoints are AEs graded using CTCAE (Version 5.0) criteria. Safety will be assessed by quantifying the toxicities and grades experienced by subjects who have received Pembrolizumab, including serious adverse events (SAEs) and events of clinical interest (ECIs). Other safety endpoints include laboratory safety assessments, KPS status, vital signs and physical examinations.

12.2.5 Analysis Population

12.2.5.1 Efficacy Analysis Populations

The Full Analysis Set (FAS) population will serve as the primary population for the analysis of efficacy data in this study. The FAS population consists of all subjects within each cohort who have received at least one dose of study treatment.

Two supportive analyses of the primary and selected secondary efficacy endpoints will be conducted. The first supportive analysis will be conducted in the FAS-2 population, defined as all subjects who meet the FAS population definition and have a post baseline scan OR discontinue the trial due to progressive disease/drug related AE. The second analysis will be conducted using the intention to treat (ITT) population, defined as all randomized subjects.

Subjects will be included in the cohort to which they are randomized for the analysis of efficacy data.

12.2.5.2 Safety Analysis Populations

The All Patients as Treated (APaT) population will be used for the analysis of safety data in this study. The APaT population consists of all allocated subjects who received at least one dose of study treatment.

At least one laboratory or vital sign measurement obtained subsequent to at least one dose of study treatment is required for inclusion in the analysis of each specific parameter. To assess change from baseline, a baseline measurement is also required.

Details on the approach to handling missing data for safety analyses are provided in Section 12.2.6 Statistical Methods.

12.2.6 Statistical Methods

Nominal p –values may be computed for efficacy analyses as a measure of strength of association between the endpoint and the treatment effect rather than formal tests of hypotheses. Unless otherwise stated, all statistical tests will be conducted at the $\alpha=0.05$ (2-sided) level.

12.2.6.1 Statistical Methods for Primary Endpoint and Efficacy Analyses

Stage 1:

A two-sample Student's t-test will be used to test the difference of TIL density between the two groups. Data distribution will be examined prior to analysis. Data transformations will be performed as deemed appropriate.

Stage 2:

A two-sample Student's t-test will be used to test the difference of cell cycle-related signature between the two groups. Data distribution will be examined prior to analysis. Data transformations will be performed as deemed appropriate.

For PFS endpoint, the analyses will be conducted using pooled Group A and Group B patients. Kaplan-Meier (KM) curves and median estimates from the KM curves will be provided as appropriate. Percent PFS6 will be estimated from the KM curves and compared to historical controls. Subjects without efficacy evaluation data or without survival data will be censored at Day 1.

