2. BACKGROUND

2.1 Study Disease

Glioblastoma is the most common primary glial neoplasm of the central nervous system in adults.¹ Despite rigorous therapeutic efforts, overall prognosis remains dismal. Specifically, multimodality therapy integrating surgery, radiation therapy and temozolomide chemotherapy is associated with a median progression-free survival of only 6.9 months, and a median overall survival of 14.6 months.² Following progression, salvage therapies have historically been of nominal benefit with PFS-6 rates under 10% noted in recent meta-analyses.³⁻⁵

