- v. Imaging: gadolinium-enhanced contrast and non-contrast MRI. CT alternative, if MRI contraindicated. Initial imaging should be performed within 14 days prior to registration. On-study imaging should be performed every 6 weeks at Day 1 of each cycle (-7 days). The same imaging technique should be used in a participant throughout the trial, if feasible. Local reading (investigator assessment) will be used to determine eligibility and for participant management.
- w. Response Assessment: Per RANO criteria (section 10).
- x. Pembrolizumab Administration: Pre-surgery pembrolizumab required for participants randomized to Group A only (14 days +/- 5 days prior to day of surgery). Post-surgery pembrolizumab must start no more than 35 days following surgery. Post surgery pembrolizumab may be administered +/- 3 days from days 1 and 22 of each cycle.
- y. Blood for tumor mRNA: please see Table 6 Correlative Sample Summary for details on collection requirements.
- z. Blood for Flow Cytometry: please see Table 6 Correlative Sample Summary for details on collection requirements.
- aa. Tumor Resection: please see Table 6 Correlative Sample Summary for details on collection requirements. On-study surgery tissue should be submitted within 60 days of surgery.
- bb. Submission of archival tissue: archival tumor tissue should be submitted within 60 days of registration. Please see section 8.3 for details.
- cc. Post-end-of-treatment oncology therapies: start/stop dates, names of treatment regimens and reason for stopping should be collected.
- dd. Survival: date of death and reason should be collected for overall survival purposes, when applicable.
- ee. For post-surgery MRI (for both Group A and B participants), if the post-surgery MRI is greater than 21 days from post-surgery pembrolizumab initiation, then MRI must be repeated.
- ff. Blood for Flow Cytometry (added in Stage 2) must be drawn 7 days after initial pembrolizumab administration (+/- 2 days). Please see Table 6 Correlative Sample Summary for details on collection requirements.

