10.2 Response/Progression Categories

10.2.1 Complete response (CR). All of the following criteria must be met:

- Complete disappearance of all enhancing measurable and non-measurable disease sustained for at least 4 weeks. In the absence of a confirming scan 4 weeks later, this scan will be considered only stable disease.
- No new lesions.
- All measurable and non-measurable lesions must be assessed using the same techniques as baseline.
- Participants must be on no steroids or on physiologic replacement doses only.
- Stable or improved non-enhancing (T2/FLAIR) lesions

- f) Stable or improved clinically, for clinical signs and symptoms present at baseline and recorded to be disease related

Participants with non-measurable disease cannot have a complete response. The best response possible is stable disease.

10.2.2 Partial response (PR). All of the following criteria must be met:

- a) Greater than or equal to 50% decrease compared to baseline in the sum of products of perpendicular diameters of all measurable enhancing lesions sustained for at least 4 weeks. In the absence of a confirming scan 4 weeks later, this scan will be considered only stable disease.
- b) No progression of non-measurable disease.
- c) No new lesions.
- d) All measurable and non-measurable lesions must be assessed using the same techniques as baseline.
- e) The steroid dose at the time of the scan evaluation should be no greater than the dose at time of baseline scan.
- f) Stable or improved non-enhancing (T2/FLAIR) lesions on same or lower dose of corticosteroids compared to baseline scan.
- g) Stable or improved, for clinical signs and symptoms present at baseline and recorded to be disease related clinically.

Participants with non-measurable disease cannot have a partial response. The best response possible is stable disease.

10.2.3 Progressive disease (PD). Any of the following criterion must be met:

- a) > 25% increase in sum of the products of perpendicular diameters of enhancing lesions (over best response or baseline if no decrease) on stable or increasing doses of corticosteroids
- b) Any new enhancing measurable lesion

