- c) Clear clinical deterioration not attributable to other causes apart from the tumor (e.g. seizures, medication side effects, complications of therapy, cerebrovascular events, infection, etc.). The definition of clinical deterioration is left to the discretion of the investigator but it is recommended that a decline in the Karnofsky Performance Score (KPS) from 100 or 90 to 70 or less, a decline in KPS of at least 20 from 80 or less, or a decline in KPS from any baseline to 50 or less, for at least 7 days, be considered neurologic deterioration, unless attributable to co-morbid events or changes in corticosteroid dose.
- d) Failure to return for evaluation due to death or deteriorating condition

10.2.4 Stable disease (SD). All of the following criteria must be met:

- a) Does not qualify for CR, PR, or progression.
- b) All measurable and non-measurable sites must be assessed using the same techniques as baseline.
- c) Stable clinically.

10.2.5 Unknown response status. Progressive disease has not been documented and one or more measurable or non-measurable lesions have not been assessed.

The RANO Response Criteria to be used in this study are summarized in Table 7.

Table 7 Summary of the RANO Response Criteria

	CR	PR	SD	PD#
T1-Gd +	None	$\geq 50\%$ decrease	$<50\%$ decrease- $<25\%$ increase	$\geq 25\%$ increase*
T2/FLAIR	Stable or decrease	Stable or decrease	NA	NA
New Lesion	None	None	None	Present*
Corticosteroids	None	Stable or decrease	Stable or decrease	Stable or increasing
Clinical Status	Stable or increase	Stable or increase	Stable or increase	Decrease*
Requirement for Response	All	All	All	Any*

CR=complete response; PR=partial response; SD=stable disease; PD=progressive disease;
NA= not applicable

#: Progression occurs when any of the criteria with * is present

Increase in corticosteroids alone will not be taken into account in determining progression in the absence of persistent clinical deterioration

Of note, patients who require increased corticosteroids within two weeks of MRI assessment (relative to the dose taken at the time of the prior assessment) cannot be classified as CR, PR or SD and should be classified as non-evaluable at that time point. Conversely, patients who decrease corticosteroids within two weeks of MRI assessment (relative to the dose taken at the time of the prior assessment) cannot be classified as PD and should be classified as non-evaluable.

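### The PFS censoring rule in 12.2.6.1 makes no exception for early death or deterioration, which 10.2.3 counts as progression; read literally, it slightly inflates PFS6

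*Combined protocol and SAP*

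**What the plan says.** Four parts of the combined protocol and SAP bear on this.

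- **Censoring rule (12.2.6.1).** In the paragraph on PFS: "Subjects without efficacy evaluation data or without survival data will be censored at Day 1". The two conditions are joined by *or*, and no exception is given. The same paragraph says: "Percent PFS6 will be estimated from the KM curves and compared to historical controls". Groups A and B are pooled.
- **Endpoint (12.2.4.1).** "Efficacy will be measured by percent PFS6 as defined by RANO".
- **Definition of progression (10.2.3).** The list of criteria is introduced by "Any of the following criterion must be met", so one is enough. Item (c) is clear clinical deterioration attributable to tumor. Item (d) is "Failure to return for evaluation due to death or deteriorating condition".
- **Population (12.2.5.1).** "The FAS population consists of all subjects within each cohort who have received at least one dose of study treatment". No post-baseline scan is required for the FAS; a scan enters only as one of the alternative conditions for the supportive FAS-2 set.

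Section 12 does not define a PFS event, does not say what counts as efficacy evaluation data, and does not say which Day 1 is meant. Footnote b of the Study Calendar uses the term both for a pre-surgery day and for the first day of later cycles.

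**The concern.** The same patient can be handled in two opposite ways. A patient who receives a dose and then dies, or becomes too ill to attend, before any assessment is a progression under 10.2.3(d). Under the literal wording of 12.2.6.1 that patient has no efficacy evaluation data and is censored at Day 1, so contributes nothing to the curve.

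Such censoring is informative, because the patients removed are the earliest failures. The bias therefore has one direction only, in favor of the treatment, and a larger sample does not remove it.

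The schedule leaves room for such cases. Group A is dosed 14 ± 5 days before surgery, restarts up to 35 days after it, and is imaged every 6 weeks from then on. From first dose to first scheduled on-treatment scan can therefore take about 19 + 35 + 42 = 96 days, with a post-surgery MRI in between that appears to serve as the response baseline. For Group B, first dosed after surgery, the interval is about 42 days.

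PFS6 is the only secondary objective (1.3), and it is to be set against historical controls, for which section 2.1 cites "PFS-6 rates under 10% noted in recent meta-analyses". Against a benchmark that low, an avoidable upward bias is unwelcome even if small.

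**Working it through.** The plan gives no target, power or event count for PFS6, so there is no figure of its own to reproduce. The check is the effect of the rule on the Kaplan-Meier estimate.

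**Inputs**
- N = 50: the planned evaluable total, 30 in Stage 1 plus 20 in Stage 2 (synopsis).
- True PFS6 = 10%: an assumption, chosen near the historical rate in section 2.1; 5% and 20% are shown as a range.
- k = number of treated patients who die or deteriorate with no evaluation: not in the documents; 1 to 5 is an assumption.

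**Formula.** Let S patients be event-free at 6 months, with no other censoring.
- Early failures counted as events: PFS6 = S/N.
- Early failures censored at Day 1: they leave before the first event, so the curve starts from N − k patients and PFS6 = S/(N − k).
- Ratio of the two: N/(N − k).

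**Results at N = 50 and 10% (S = 5)**

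| k | Factor | PFS6 under Day 1 censoring | Shift (points) |
|---|---|---|---|
| 0 | 1.000 | 5/50 = 10.0% | 0 |
| 1 | 50/49 = 1.020 | 5/49 = 10.2% | +0.2 |
| 3 | 50/47 = 1.064 | 5/47 = 10.6% | +0.6 |
| 5 | 50/45 = 1.111 | 5/45 = 11.1% | +1.1 |

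A direct Kaplan-Meier calculation on constructed event times gave the same values.

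**Against sampling error.** Standard error at 10% = √(0.10 × 0.90/50) = 4.24 points. The largest shift is 1.11/4.24 = 0.26 standard errors.

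**Range over the assumed true PFS6 (N = 50, k = 1 to 5)**
- 5%: 5.1% to 5.6%, standard error 3.08 points.
- 20%: 20.4% to 22.2%, standard error 5.66 points, so at most 2.22/5.66 = 0.39 standard errors.

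**Range over N (true PFS6 10%)**
- N = 30, Stage 1 alone: 3/29 = 10.3% (k = 1) to 3/25 = 12.0% (k = 5).
- N = 60, from the 35 patients reported as enrolled in section 1.1 plus up to 25 in Stage 2: 6/55 = 10.9% at k = 5.

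**The case against.** The best defense is that the sentence was only meant for patients about whom nothing is known. If PFS6 follows RANO, and non-return through death or decline is itself progression under 10.2.3(d), then a patient so classified has efficacy data and is not caught by the rule. The reference to survival data would then apply to OS only. Other sections point the same way:

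- 10.1.2 keeps patients who progress or die before the end of cycle 1 evaluable for objective response.
- 5.12 counts patients who discontinue for progressive disease in the evaluable population.
- The FAS-2 definition in 12.2.5.1 admits patients without a scan who discontinue for progression.

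These passages make the intention fairly clear. None of them states the PFS rule, though, and none overrides a sentence that does. The wording also has a second literal effect: a patient with progression documented on a scan but without survival data would be censored at Day 1 as well.

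It can also be said that k should be small. A declining patient who is still seen in clinic can be classified under 10.2.3(c), end-of-treatment assessments are due within 7 days of the decision to stop (Study Calendar, footnote d), and Group B patients who fail before their first dose are outside the FAS. This stands, and it makes the upper end of the assumed range less likely. It limits the size of the bias but does not change its direction.

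Finally, this is a pilot trial, PFS6 is an estimate with no decision threshold, and section 12.2.6 treats efficacy p-values as nominal. That also stands, and it is why the point is modest.

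**Conclusion.** The concern holds. As written, 12.2.6.1 conflicts with the progression definition on which PFS6 rests, and an analyst who follows it to the letter will overstate PFS6. At N = 50 and a true PFS6 of 10%, the overstatement is 0.2 to 1.1 points for k = 1 to 5, at most about a quarter of a standard error. Under the alternative reading it is zero.

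The size rests on the assumed k, the assumed true rate and no other censoring. The direction does not depend on the values chosen, provided at least one early failure is censored and at least one patient is event-free at 6 months. The TIL density and cell cycle signature endpoints, and their power calculations, are not affected.

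The sentence should be corrected before analysis, because in an open-label trial the choice between the two readings should not be left until the data are known.

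**What to change.** Replace the sentence in 12.2.6.1 with text such as:

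> For PFS, death from any cause, or progressive disease under 10.2.3 including items (c) and (d), is an event on its date even if no post-baseline scan was done. Subjects with no post-baseline assessment and no such event, including those whose vital status is unknown, are censored at Day 1.

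Limit the clause on missing survival data to OS, and state which day Day 1 is.

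The cost is a short SAP edit. No new data are needed: the Study Calendar already provides that "date of death and reason should be collected for overall survival purposes" (footnote dd), and clinical status is recorded at study visits. No treatment rule changes. The only downside is a PFS6 that may come out slightly lower.

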12.2.6.2 Statistical Methods for Safety Analyses

Safety and tolerability will be assessed by clinical review of all relevant parameters including adverse experiences (AEs), laboratory tests, and vital signs. Safety summaries will be reported for both cohorts.

Immune related adverse experiences (irAEs, as defined in Section 7.3.2) are prespecified as events of interest. These events will be summarized in separate tables from other AEs by toxicity grade and will include the counts, percentage, and 95% CI. Any AE of unknown etiology associated with pembrolizumab exposure will be evaluated to determine if it is possibly an event of clinical interest (ECI) of a potentially immunologic etiology (irECI). Other ECIs listed in section 7.3.2 will also be summarized in the same manner as irAEs.

Adverse experiences (specific terms as well as system organ class terms) and predefined limits of

change in laboratory, and vital sign parameters that are not pre-specified as events of interest will be summarized with descriptive statistics (counts, percentage, mean, standard deviation, etc.).

Continuous measures such as changes from baseline in laboratory, and vital signs parameters that are not pre-specified as events of interest will be summarized using descriptive statistics (mean, standard deviation, etc.) for baseline, on-treatment, and change from baseline values.

12.2.6.3 Statistical Methods for Exploratory Analyses

Variables involved in exploratory analyses will be examined graphically and summarized by descriptive statistics. Data transformation may be applied to quantitative variables prior to analyses if deemed necessary.

Bivariate association analyses will be conducted to evaluate the associations between exploratory biomarkers and clinical outcomes and adverse events for the objectives listed in 1.4. The analyses will be performed for each group separately and/or combined as deemed appropriate. Specifically, Pearson or Kendall's tau correlation coefficients will be calculated to evaluate the association between quantitative variables, Chi-squared tests or Fisher's exact tests will be used to examine the association between categorical or ordinal variables, and ANOVA will be performed to study the association between a quantitative variable and a categorical variable. The association between biomarkers and clinical outcomes (PFS and OS) will be evaluated using Cox regression. For markers with multiple measurements over time, data at a specific time point or change from pre-treatment will be used in the above bivariate analyses as deemed appropriate.

Changes in markers pre- and post-treatment will be assessed using paired t-tests.

Between-group comparisons will be conducted for PFS, OS, and PD-1, PDL-1 IHC expression. Survival analyses via Kaplan-Meier curves and log-rank tests will be used to estimate and compare PFS, second PFS, and OS between Group A and Group B. PD-1 and PDL-1 IHC expression will be compared between Groups A and B using two-sample t-tests.

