1.4 Exploratory Objectives

1.4.1 Objective: To evaluate the associations between exploratory biomarkers and clinical outcomes and adverse events these include:

- 1.4.1.1** Estimate correlation of quantitative assessments of TIL density or clonality with clinical responses to pembrolizumab in recurrent glioblastoma patients.
- 1.4.1.2** Estimate efficacy of pembrolizumab by PFS, second PFS and OS. (Groups A and B) as defined by RANO.
- 1.4.1.3** Estimate efficacy of pembrolizumab by PFS6, PFS, second PFS and OS. (Groups A and B) as defined by iRANO.
- 1.4.1.4** Explore effect of pembrolizumab on TIL proliferation (CD8+KI-67+ staining).
- 1.4.1.5** Estimate difference in PD-1 and PDL-1 IHC expression between Group A and B as well as between archived and study samples.
- 1.4.1.6** Explore whether oligoclonal T cell populations within tumor tissue are similarly expanded in peripheral blood after pembrolizumab, the magnitude of which correlates with clinical responses.
- 1.4.1.7** Explore if changes in specific MRI parameters correlate with tumor and peripheral blood immune responses.
- 1.4.1.8** Correlation of tumor mRNA from extracellular vesicles with outcome.

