5. TREATMENT PLAN

This is a pilot surgical trial to evaluate early immunologic pharmacodynamic parameters for the PD-1 checkpoint inhibitor, pembrolizumab (MK-3475), in patients with surgically accessible recurrent/progressive glioblastoma. The principle goal of this study is to understand, in surgically resectable recurrent/progressive GBM, if neoadjuvant pembrolizumab elicits a systemic immunologic response, a tumoral immunologic response and toxicity and if that response can be correlated with other non-invasive measures of pembrolizumab bioactivity (tumor, blood, imaging, and clinical outcomes). The study includes 2 stages, in the first stage (**Stage 1**), for optimal understanding of the effect of the drug on tumor tissue patients will be randomized in to Group A or Group B. In the second stage (**Stage 2**), additional patients will be enrolled to an expansion arm of Group A only to specifically study the effect of the drug on cell cycle/cancer proliferation related genetic signature.

Stage 1:

Groups A and B: Patients will be randomly assigned to either group A or B with a 1:1 randomization ratio prior to surgery. Patients in all groups will receive the study drug pembrolizumab after tumor resection. Only Group A will receive a single infusion of pembrolizumab of 200mg 14± 5 days prior to surgery (when scheduling, please keep in mind that the two pre-surgical plasma samples should be drawn greater than 10 days apart - see Table 6 for full details). Group B will not receive study drug prior to surgery. **This randomization scheme should not negatively impact study accrual and will provide an invaluable control cohort for PD evaluations.**

Group A: Neoadjuvant/adjuvant evaluation: Fifteen eligible patients will receive a single infusion of pembrolizumab of 200mg 14± 5 days prior to scheduled surgical resection for

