TIL Density and TCR Overlap ([name]/[name]/[name], UCLA)	TCR ImmunoSeq and TCR Overlay (Adaptive Biotech.) on tumor tissue and peripheral blood mononuclear cell genomic DNA	Tumor (protocol surgery) and peripheral blood (Pre-Tx, Post-Tx)	200 mg of fresh tissue (approximately 20% tumor nuclei) sent in 2 mL Allprotect ® tissue reagent (Qiagen) or RNA-later® reagent Pre-treatment and post-treatment PBMC can be used from blood collected for flow cytometry (see below)	[name]. C/O [name] [name] [name] Los Angeles, CA 90095 [contact] Email: [contact] and [contact]
IHC measurements ([name]/[name]/[name], UCLA)	PD-1/PD-L1/CD8/CD4/CD8/Iba-1/CD68/GFAP IHC on FFPE tumor tissue	Archived and protocol surgery from tumor block	Archived: 1 formalin-fixed paraffin embedded (FFPE) tumor tissue block (preferred) from most recent surgery revealing glioblastoma Protocol Surgery: 1 FFPE tumor tissue block (preferred) or a minimum of 10 FFPE unstained sections	[name]. C/O [name] [name] [name] Los Angeles, CA 90095 [contact] Email: [contact] and [contact]
Peripheral blood T cell subsets/activation markers ([name]/[name]/[name], UCLA)	Flow Cytometry on peripheral blood mononuclear cells	Peripheral blood (Pre-surgery pre-treatment, pre-surgery post treatment, with every MRI)	Pre-surgery pre treatment blood (for Groups A and B) : 10 Green top tubes (10ml/tube – sodium heparin tubes preferred) following registration/randomization and pre-pembrolizumab for Group A Pre-surgery, day 7 post pembrolizumab administration (+/- 2 days): 10 Green top tubes 10-ml sodium heparin tubes preferred (should not be same timepoint as next 'pre-surgery post treatment' blood) Pre-surgery: 10 Green top tubes 10ml – sodium heparin tubes preferred (should be greater than 10 days from initial dose of Pembrolizumab for Group A – Group B should also have a sample drawn pre-surgery, greater than 10 days from initial sample)	[name]. C/O [name] [name] [name] Los Angeles, CA 90095 [contact] Email: [contact] and [contact]

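### Blood markers, and IHC markers other than PD-1/PD-L1, have no planned Group A versus Group B comparison: change is tested only by paired t-tests, although Group B supplies matching drug-free sample pairs

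*Combined protocol and SAP*

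**What the plan says.** Section 5 states the principal goal as learning "if neoadjuvant pembrolizumab elicits a systemic immunologic response, a tumoral immunologic response and toxicity". It justifies randomisation on the ground that Group B "will provide an invaluable control cohort for PD evaluations".

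Sampling follows that logic. Section 5 and Table 6 require two pre-surgical blood draws in both groups. For flow cytometry, Table 6 adds that "Group B should also have a sample drawn pre-surgery, greater than 10 days from initial sample". Both groups also provide an archived block and protocol-surgery tissue for IHC. Table 6 lists CD4, CD8, Iba-1, CD68 and GFAP alongside PD-1 and PD-L1.

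The analysis text in 12.2.6.3 has three relevant parts:

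- Change: "Changes in markers pre- and post-treatment will be assessed using paired t-tests". Neither the group nor the sample pair is stated.
- Between groups: "Between-group comparisons will be conducted for PFS, OS, and PD-1, PDL-1 IHC expression". Second PFS is added in the next sentence, and for IHC "PD-1 and PDL-1 IHC expression will be compared between Groups A and B using two-sample t-tests".
- Serial markers: "data at a specific time point or change from pre-treatment will be used in the above bivariate analyses as deemed appropriate". The analyses referred to are associations of biomarkers with clinical outcomes and adverse events, not Group A versus Group B.

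Objective 1.4.1.5 reads "Estimate difference in PD-1 and PDL-1 IHC expression between Group A and B as well as between archived and study samples". Section 12.2.6 sets a two-sided 5% level by default.

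**The concern.** The systemic half of the Section 5 goal rests on blood. For blood, the only named test of change is within-patient, and a within-patient test asks whether the mean moved, not why. Between the two pre-surgical draws, tumour course, steroid adjustment (Section 5.8.1 discourages more than 4 mg/day before surgery but allows for it) and assay variation can all move a lymphocyte subset. Between the archived block and the protocol surgery, progression intervenes, and prior radiation or chemotherapy may too, depending on when the block was taken.

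Group B goes through the same intervals without drug, so it measures that background movement. If the comparison with Group B is not made, the trial could report a significant change in Group A that Group B also shows, and the randomised control would go unused for these markers.

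**Working it through.** **1. Which markers have a Group A versus Group B test?**

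| Marker | Paired samples | A versus B test in the plan |
|---|---|---|
| TIL density (Stage 1 primary) | protocol-surgery tumour only | yes, 12.2.6.1 |
| Cell cycle signature (Stage 2 primary) | protocol-surgery tumour only | yes, 12.2.6.1 |
| PD-1/PD-L1 IHC | archived and surgery | yes, on levels, 12.2.6.3 |
| Other IHC markers | archived and surgery | none named |
| Flow-cytometry subsets | two pre-surgical bloods | none named |
| Extracellular-vesicle mRNA | two pre-surgical plasmas | none named |

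The gap is the last three rows.

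**2. The plan's own figure.** Section 12.2.3 gives 15 per group, a difference of 0.5, an SD of 0.5 and one-sided alpha of 0.05, with 85% power. The standardised effect is 0.5/0.5 = 1.0. Noncentrality is 1.0 × √(15×15/30) = 2.739, on 28 df, with critical value 1.701. Noncentral-t power is 84.8%, which reproduces the stated 85% and confirms the group size used below. No power is stated for the paired tests.

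**3. The paired test when the drug does nothing.** Let δ be the drift in SDs of the within-patient change. The documents give neither a drift nor an SD of change, so δ is assumed. Noncentrality is δ√n, and the test is two-sided at 5%.

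| n in Group A | δ | δ√n | critical t | P(significant) |
|---|---|---|---|---|
| 15 | 0 | 0 | 2.145 | 5% |
| 15 | 0.25 | 0.968 | 2.145 | 15% |
| 15 | 0.3 | 1.162 | 2.145 | 19% |
| 15 | 0.5 | 1.936 | 2.145 | 44% |
| 35 | 0.3 | 1.775 | 2.032 | 41% |
| 35 | 0.5 | 2.958 | 2.032 | 82% |

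The n = 35 rows additionally assume that Stage 1 and Stage 2 Group A patients (15 + 20) are pooled for this test, which the plan does not say.

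**4. The between-group test of change.** Drift common to both groups cancels, so with no drug effect the rejection rate is 5% for any δ. Simulation (20,000 trials, 15 versus 15, drift 0 to 0.8 SD) gave 4.9% to 5.1%.

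**5. Power of that test for a real effect.** Noncentrality is d × √7.5 = 2.739d, on 28 df, with two-sided critical value 2.048.

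| True effect (SD of change) | Noncentrality | Power, unadjusted |
|---|---|---|
| 0.5 | 1.369 | 26% |
| 0.8 | 2.191 | 56% |
| 1.0 | 2.739 | 75% |

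**6. What baseline adjustment adds.** With equal variances and correlation r between the two samples, the variance of the change is 2(1−r)σ² and the ANCOVA residual variance is (1−r²)σ². The ratio is (1+r)/2. At an assumed r = 0.5 it is 0.75, so noncentrality rises by 1/√0.75 = 1.155. On 27 df, power becomes about 33%, 68% and 86%.

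**The case against.** Several points against the concern stand, and they set its limits.

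- A reader might infer that all pre-to-post change is uncontrolled. It is not: PD-1/PD-L1, TIL density and the cell cycle signature each have a Group A versus Group B test. For PD-1/PD-L1, comparing surgery levels among the Stage 1 randomised patients already protects against a shared disease course. Leaving out the archived value costs precision, not validity.
- A reader might infer that radiation and temozolomide confound the blood changes. The documents do not support this. Both pre-surgical bloods follow registration, the washouts in Section 3.1 precede it, and Section 5.7.2 prohibits radiation and non-protocol chemotherapy during screening and treatment. These exposures can matter only for the archived-to-surgery tissue pair.
- A reader might infer that the plan attributes paired changes to pembrolizumab. It says only that they will be assessed. If drift is real, rejecting the paired null of no mean change is correct. The error would lie in the attribution.
- Objective 1.4.1.5 asks for the archived-versus-study difference, so that paired estimate has a purpose and should stay.
- The drift sizes are assumptions. The analyses are exploratory, and Section 12 allows exploratory methods to change if the clinical study report explains why.

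None of this supplies a controlled comparison for the blood markers or the remaining IHC markers. The provision for using change from pre-treatment covers associations with outcomes and adverse events, so it does not fill the gap.

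**Conclusion.** The concern holds for flow-cytometry subsets, extracellular-vesicle mRNA and IHC markers other than PD-1/PD-L1. For these, 12.2.6.3 names only a within-patient test, leaves the pre and post samples undefined, and does not use the drug-free pairs that Group B provides. With 15 patients and no drug effect, the paired test would be significant in 19% or 44% of trials at a drift of 0.3 or 0.5 SD of change, against 5% for a randomised comparison. Those percentages illustrate the exposure under assumed drift and do not estimate what will happen in this trial. The gap bears on how a systemic immune response can be interpreted. It does not touch the primary endpoints or PFS6. The change should be made, because the samples exist and the systemic response is part of the stated principal goal.

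**What to change.** In 12.2.6.3:

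1. Define the pre and post sample for each marker in each group.
2. For blood markers and IHC markers other than PD-1/PD-L1, add an ANCOVA in the Stage 1 randomised patients: pre-surgery (or protocol-surgery) value on baseline (or archived) value plus group. Take the group difference as the estimate of the pembrolizumab effect.
3. Report paired changes by group as descriptive, including the archived-versus-study comparison in objective 1.4.1.5.
4. Label Stage 2 Group A changes, the Day 7 blood sample and all post-surgery changes as uncontrolled. Stage 2 has no randomised control, and Group B receives drug after surgery.
5. Keep the existing Group A versus Group B comparison of PD-1/PD-L1. Adjusting it for the archived value is an optional gain in precision.

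No new samples are needed, so the work is SAP wording and a few model fits. The real cost is modest power for the controlled test, as shown in the working, of which baseline adjustment recovers part. Results should therefore be given as estimates with confidence intervals, and a non-significant difference should not be read as absence of effect.
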